Part B is a randomized, double-blind, placebo-controlled, parallel group, dose-finding investigation to evaluate the efficacy, safety, and immunogenicity of izokibep in subjects with moderate to severe HS. Subjects will complete up to a 28-day screening period, followed by a 16-week double-blind treatment period. At completion of the Week 16 visit procedures, subjects randomized to placebo will be switched to active treatment in a blinded manner for the Week 16 dose through Week 30 (Q2W dose group) or Week 31 (QW dose group). Subjects randomized to izokibep will remain on the same dose through Week 30 (Q2W dose

group) or Week 31 (QW dose group). After their respective treatment periods, all subjects will enter a follow-up period that includes 2 visits to be completed at Week 39 and Week 45. For subjects that early terminate the follow-up visits should be completed 8-weeks (\pm 5 days) and 14 weeks (\pm 5 days) after the last dose of study drug.

Approximately 170 subjects will be randomized into 1 of 4 groups in a 1:1:2:2 ratio as follows:

- Group 1 (n = 28-29): placebo SC QW from Day 1 (Week 0) to Week 15, then izokibep SC 160 mg QW from Week 16 to Week 31.
- Group 2 (n = 28-29): placebo SC Q2W from Day 1 (Week 0) to Week 14, then izokibep SC 160 mg Q2W from Week 16 to Week 30.
- Group 3 (n = 56-57): izokibep SC 160 mg QW from Day 1 (Week 0) to Week 31.
- Group 4 (n = 56-57): izokibep SC 160 mg Q2W from Day 1 (Week 0) to Week 30.

Randomization will be stratified by any prior biologic/Janus Kinase (JAK) inhibitor used for HS (Yes/No) and Hurley Stage (II or III).

Subjects will complete study assessments according to the study visits outlined in the SoA in the protocol. Day 1 corresponds to the first dose of study drug. All subsequent visits will be scheduled based on the Day 1 visit.

Subjects in the QW dosing groups (Group 0 [Part A], Groups 1 and 3 [Part B]) will have study visits at screening, Day 1 (Week 0), and at Weeks 1, 2, 3, 4, 8, 12, 13, 14, 15, 16, 17, 20, 24, 28, and 32 as well as at the follow-up visits.

Subjects in the Q2W dosing regimens (Groups 2 and 4 in Part B) will have study visits at screening, Day 1 (Week 0), and at Weeks 2, 4, 8, 12, 14, 16, 18, 20, 24, 28, and 32 as well as at the follow-up visits.

Subjects assigned to placebo SC QW and placebo SC Q2W will be grouped into a single placebo group for comparison to each dosing regimen of izokibep for Part B. The primary endpoint will be assessed at Week 16.

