3.1.4. Handling of Intercurrent Events to Reflect the Clinical Question of Interest

The treatment policy strategy approach for the estimand will be used in general, so subjects will be included using observed data at Week 16 regardless of treatment compliance, use of rescue medications except as noted below, or any other protocol deviation. Subjects with missing HiSCR75 assessments at Week 16 will be imputed as non-responders (non-response imputation or NRI). A composite strategy will be used for intercurrent events of receiving oral antibiotic therapy that could affect HS: a list of all subjects who received oral antibiotic therapy that results in such imputation will be finalized after review of all oral antibiotic therapy received by any subject and before unblinding of the study, and will include any subject who initiated a new regimen of tetracycline, clindamycin, and possibly other products, and any subject who was on a stable dose of minocycline or doxycycline at randomization but received a higher dose during the study. The endpoint for such subjects will be imputed using NRI.

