6.6.1. Primary Efficacy Analysis

The primary efficacy variable is defined as HiSCR75, the proportion of subjects who achieve at least a 75% reduction from baseline in the total AN count, with no increase from baseline in abscess or draining fistula count at Week 16 (comparing to baseline).

For Part B, the statistical null and alternative hypotheses to be used to assess the primary objective are:

> H₀: $\pi_{ABY} - \pi_{PBO} = 0$ H_A: $\pi_{ABY} - \pi_{PBO} \neq 0$

where π_{ABY} and π_{PBO} are the proportion of subjects achieving HiSCR75 at Week 16 among subjects randomly assigned to receive izokibep and placebo, respectively. One set of hypotheses will be tested for each dosing frequency of izokibep.

The treatment policy strategy approach for the estimand will be used in general, so subjects will be included using observed data at Week 16 regardless of treatment compliance, use of rescue medications or procedures except as noted below, or any other protocol deviations. Subjects with missing HiSCR75 assessments at Week 16 will be imputed as non-responders (non-response imputation or NRI). A composite strategy will be used for intercurrent events of receiving oral antibiotic therapy that could affect HS. A list of all oral antibiotic therapy that results in such imputation will be finalized after review of all oral antibiotic therapy received by any subject and before unblinding of the study and will include tetracycline, clindamycin, and possibly other products. Such subjects will be imputed using NRI. The Page 37 of 75 Final, Version 3.0, 03APR2024

ST-AD-008 version 06

number of subjects imputed with NRI will be tabulated with reasons for imputation at Week 16. Additionally, any lesions that received lesional incision and drainage or intralesional steroid injection will be counted as continuing to exist in the AN count, even if fully healed, at all later timepoints.

The null hypothesis of equal response rates will compare each dosing regimen of izokibep to the combined placebo group.

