6.6.7. Post-Week 16 (Part B, Period 2) Additional Analyses

The following analyses will be done for all four randomized treatment groups in the FAS:

- Proportion with at least 3 points reduction from baseline in NRS in Patient Global Assessment of Skin Pain at its worst, among subjects with baseline NRS ≥ 4, at weeks 24 and 32 will be summarized by number and proportion along with Clopper-Pearson 95% CI without strata according to the four randomized treatment groups.
 - NRI will be handled analogously to the corresponding secondary endpoint analysis, except subjects who took Tramadol as allowed per-protocol (at a dose of up to 100 mg po every 4 hours, not to exceed 400 mg per 24 hours) during the 28 days prior to the visit will not be counted as a non-responder.
- Descriptive MMRM analyses will be performed by randomized treatment group, for the continuous endpoints described below. The measured value at the visit will be used as the response variable, with visit week, treatment, and treatment * visit week interaction included as predictors. The model will include all visits from Day 1 through Week 32. Unstructured covariance matrix will be used. Other variance-covariance matrices, such as autoregressive, and compound-symmetric will be considered if the model does not converge. Estimated LSMean, corresponding SE values, and 95% confidence intervals will be summarized at the timepoints defined below.
 - Modified Sartorius Score at Weeks 24 and 32;
 - NRS PGA of Skin Pain (at its worst and average respectively) at Weeks 24 and 32. To maintain consistency between all visits, only the score collected on the visit day will be used for this analysis.
 - Draining fistula count at Weeks 24 and 32;
 - EQ-5D at Weeks 24 and 32;
 - DLQI at Weeks 24 and 32;
 - HADS, HADS-anxiety, and HADS-depression at Weeks 24 and 32;
 - IHS4 scores at Weeks 24, and 32

These summaries will address the question of expected results if a subject is assigned to either 32 weeks of izokibep or 16 weeks of placebo followed by 16 weeks of izokibep.

- A time-to-event analysis using Kaplan-Meier (KM) curves by randomized treatment group will be created for the events listed below.). If estimable, quartiles of the time to each event will be summarized by randomized treatment group. Product limit estimate at Week 32 (Day 224) will be provided. Participants will be censored at the time of last recorded assessment on study:
 - First achievement of HiSCR75
 - First achievement of HiSCR100

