 - First achievement of HiSCR90
 - First achievement of HiSCR50

- First achievement of AN count of 0, 1, or 2 for subjects with baseline Hurley Score II
- First achievement of ≥ 3 point reduction in NRS in Patient Global Assessment of Skin Pain at its worst among subjects with baseline NRS ≥ 4
 - To maintain consistency between all visits, only the score collected on the visit day will be used for this analysis.

These graphics will address the question of whether subjects originally randomized to placebo catch up in efficacy to the subjects who were randomized to izokibep by week 32.

The following analyses will be done by all four randomized treatment groups for the FAS subjects who had at least one dose of izokibep on or after Week 16. The analyses in subjects who received izokibep for the first 16 weeks will be done to address the question of whether responders/non-responders in the first 16 weeks of treatment experience subsequent sustained or added benefit in the following 16 weeks of treatment. The analyses in subjects who received placebo for the first 16 weeks will be done to evaluate if there is additional benefit after initial placebo response, or if placebo non-responders catch up to the subjects receiving 32 weeks of izokibep.

- The subgroup of subjects who were responders by HiSCR75 at Week 16 will be further evaluated by randomized treatment group at Week 24 and Week 32:
 - Response rate for HiSCR75, HiSCR100, HiSCR90, HiSCR50 will be summarized by randomized treatment group at Week 24 and Week 32. The responder proportions and Clopper-Pearson 95% CI without strata will be presented. The NRI approach to missing data will be the same as for the primary analysis.
 - Response rate for AN count of 0, 1, or 2 among those with Hurley stage II at baseline will be summarized by randomized treatment group at Week 24 and Week 32. The responder proportions and Clopper-Pearson 95% CI without strata will be presented. NRI approach will be the same as for the primary analysis.

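### The Kaplan-Meier curves of first response in SAP 6.6.7 put the Week 32 figures above the proportion of randomized subjects who achieve response, and can distort the catch-up comparison in either direction

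*SAP*

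**What the plan says.** The first block of SAP 6.6.7 opens with "The following analyses will be done for all four randomized treatment groups in the FAS". The set therefore includes placebo subjects who leave before the switch. The restriction to subjects dosed with izokibep on or after Week 16 begins only with the next block. For the curves of first achievement the rule is "Participants will be censored at the time of last recorded assessment on study", and "Product limit estimate at Week 32 (Day 224) will be provided". The stated purpose is to show "whether subjects originally randomized to placebo catch up in efficacy to the subjects who were randomized to izokibep by week 32".

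Under SAP 2.1, "subjects randomized to placebo will be switched to active treatment in a blinded manner for the Week 16 dose".

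Elsewhere the SAP counts leavers as failures on these endpoints:

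- SAP 6.6.1: "Subjects with missing HiSCR75 assessments at Week 16 will be imputed as non-responders".
- SAP 3.1.4: "A composite strategy will be used for intercurrent events of receiving oral antibiotic therapy that could affect HS", with those subjects set to non-response.
- SAP 3.3 and 6.6.5 carry the primary and secondary strategies over to exploratory endpoints, and SAP 6.6 presents binary endpoints with non-response imputation (NRI).
- Within 6.6.7, the Week 24 and Week 32 pain proportions use NRI. For the HiSCR response rates in Week 16 responders, "The NRI approach to missing data will be the same as for the primary analysis".

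The Kaplan-Meier bullet mentions neither NRI nor antibiotics. Stopping study drug does not by itself lead to censoring, because Protocol 7.1 encourages such subjects to stay for assessment.

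**The concern.** Leaving the study ends any chance of an observed response. The product-limit estimator instead treats a leaver as someone whose later course is merely unseen, and shares that subject's probability among those who remain. In the placebo groups the response rate should rise after Week 16, because those who remain switch to izokibep. A placebo subject censored at Week 8 is then given a post-switch response rate without having switched.

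At stake is how the Week 32 figure is read. A reader will take it as the share of the randomized group that has responded by then. It is higher than that share whenever some subjects leave without responding and others respond later. The figure is also offered as the answer to the catch-up question, so its effect on the difference between groups matters as well as its effect on each curve.

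**Working it through.** **Inputs from the documents.** Lesion counts after baseline are at Weeks 4, 8, 12, 16, 24, 28 and 32 (Protocol 1.3). Group sizes are 28-29 in each placebo group and 56-57 in each izokibep group (SAP 2.1). The documents state no figure for these curves, no dropout rate and no Period 2 response rate, so there is no plan figure to reproduce on this point. The nearest one, about 80% power for 15% versus 40% with 55 per group (SAP 2.3), does reproduce: Fisher's exact test at two-sided 0.0499 gives 79.8%.

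**Assumptions, first set.** First HiSCR75 is reached by 20% on placebo by Week 16 and by 45% of the rest by Week 32; on izokibep by 45% and then 25%. Loss is non-informative and occurs before each visit, at a constant rate within each period. The Week 32 visit counts in the Day 224 estimate.

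**Formulas.** With 4 visits in Period 1 and 3 in Period 2, the per-visit hazard is h = 1 − (1 − r)^(1/m), and likewise for loss. S is the product of (1 − h) and G the product of (1 − loss).

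- Kaplan-Meier at Week 32: 1 − S. Placebo 1 − 0.80 × 0.55 = 56.0%; izokibep 1 − 0.55 × 0.75 = 58.75%.
- Proportion achieving response, with leavers kept in the denominator: the sum over visits of S(previous visit) × G(this visit) × h(this visit).

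**Placebo, 10% loss before Week 16 and 8% after.** h = 1 − 0.80^(1/4) = 0.0543, then 1 − 0.55^(1/3) = 0.1807. Retention per visit is 0.90^(1/4) = 0.9740, then 0.92^(1/3) = 0.9726.

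- Period 1: 0.0528 + 0.0487 + 0.0448 + 0.0413 = 0.1877
- Period 2: 0.1265 + 0.1008 + 0.0803 = 0.3077
- Total 0.4954, against 0.560 by Kaplan-Meier: +6.5 points

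| Loss before/after Week 16 | Placebo KM | Placebo achieving | Excess | Izokibep KM | Izokibep achieving | Excess |
|---|---|---|---|---|---|---|
| 5%/5% | 56.0 | 52.5 | 3.5 | 58.75 | 56.3 | 2.4 |
| 10%/8% | 56.0 | 49.5 | 6.5 | 58.75 | 54.1 | 4.7 |
| 15%/10% | 56.0 | 46.8 | 9.2 | 58.75 | 51.9 | 6.8 |

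**Effect on the gap (izokibep minus placebo).** The Kaplan-Meier gap is 58.75 − 56.00 = 2.75 points throughout. Placebo loss is held at 10%/8%, with 49.54% achieving; izokibep loss after Week 16 is 8%.

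| Izokibep loss before Week 16 | Gap in proportion achieving | Shift caused by KM |
|---|---|---|
| 5% | 56.07 − 49.54 = 6.53 | 3.8 towards catch-up |
| 10% | 54.09 − 49.54 = 4.55 | 1.8 towards catch-up |
| 15% | 52.08 − 49.54 = 2.54 | 0.2 away from catch-up |
| 20% | 50.05 − 49.54 = 0.51 | 2.2 away from catch-up |

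With equal 10%/8% loss and an izokibep Period 2 response of 40% instead of 25%, the shift towards catch-up falls to 0.6 points; at 45% it is 0.2.

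**Against sampling error.** In the equal-loss base case the Greenwood standard errors are 7.1 (placebo, n = 57), 10.1 (placebo, n = 28) and 6.9 (izokibep, n = 57). The standard error of the gap is √(7.1² + 6.9²) = 9.9, or √(10.1² + 6.9²) = 12.2 with the placebo groups plotted separately, as planned. The 1.8-point shift is 0.18 or 0.15 of these.

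**Second set, starting from the SAP's 15% and 40% at Week 16.** Assume 40% of switched placebo subjects still at risk respond in Period 2, and loss occurs only before Week 16. Placebo Kaplan-Meier is 1 − 0.85 × 0.60 = 49.0%, against 44.7% achieving with 10% loss (+4.3) and 40.3% with 20% loss (+8.7). With equal loss of 10% or 20%, the gap shifts towards catch-up by 1.7 or 3.3 points if 5% of izokibep subjects still at risk respond in Period 2, and by 1.1 or 2.1 points at 15%. At 40% it shifts away by 0.4 or 0.9. With 20% loss on placebo and 10% on izokibep, the shift is 3.9 to 6.0 points towards catch-up; with the losses exchanged, it is 1.1 to 5.3 away.

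**The case against.** Four objections carry weight.

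- **Kaplan-Meier answers a recognised question.** If censoring is non-informative, it estimates the chance of ever responding when everyone is followed through the assigned sequence. That stands as a possible aim, but the SAP does not state it, and its strategies for HiSCR and AN count are treatment policy plus composite.
- **The non-response answer is already planned.** SAP 6.6.5 gives HiSCR and AN proportions at Weeks 24 and 32 by the four randomized groups with the primary strategies, and 6.6.7 does so for pain. This lowers the priority. It does not correct the curves, because response at a visit and response at any time so far are different quantities. For the same reason, a difference between the two reports is not in itself a contradiction.
- **The curves are descriptive.** No p-value is specified for them, and they lie outside the testing sequence. This stands.
- **Cumulative incidence is not NRI.** A subject who responds at Week 8 and then withdraws is an achiever under the first and a Week 32 non-responder under the second. This also stands: the fix agrees with NRI on subjects who leave without a prior response, and goes no further.

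A reader might infer that the curves overstate catch-up. The documents do not support that. The same censoring raises the izokibep curves, and the net direction turns on relative loss and on izokibep's Period 2 response, neither of which is given. A reader might also infer that a response after an HS-affecting antibiotic will count as achievement. That rests only on the bullet's silence, and SAP 3.3 and 6.6.5 may already exclude it.

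**Conclusion.** The point holds as a low-priority correction. With the stated censoring rule, the Week 32 product-limit estimate exceeds the proportion of randomized subjects who achieve response, in any group where some leave without responding and others respond later. In the placebo groups part of the excess comes from giving post-switch response rates to subjects who never switched. This departs from the NRI and composite handling that the SAP sets for the same endpoints.

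The size rests on assumed loss and response rates. For placebo it is about 3.5 to 9 points for loss of 5%/5% to 15%/10%, and the second set of assumptions gives 4.3 to 8.7. If leavers are mainly poor responders, the Kaplan-Meier figures are too high even for the no-dropout question. The effect on the catch-up gap is smaller with equal loss, 1.8 points in the base case or under a fifth of a standard error, and it reverses when izokibep loses more subjects. The direction cannot be known in advance.

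**What to change.** In SAP 6.6.7:

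1. Report the Week 32 figure in all groups as the cumulative incidence of first response. Subjects who withdraw or die without a prior response stay in the denominator as non-achievers through Day 224.
2. State that the rule on HS-affecting oral antibiotics applies to the HiSCR and AN endpoints as in the primary analysis.
3. Keep the Kaplan-Meier curve as a supplementary display, labelled as the hypothetical estimate with no dropout.

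The cost is a few sentences in the SAP and a few lines of code. Reported Week 32 achievement rates will be slightly lower.

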2.4. Primary Efficacy Variable

The primary efficacy variable for Part A and Part B is HiSCR75, the proportion of subjects who achieve at least a 75% reduction from baseline in the total AN count, with no increase from baseline in abscess or draining fistula count. The primary timepoint for analysis is Week 12 for Part A and Week 16 for Part B.

HiSCR50/75/90/100 is defined as meeting all three criteria below:

- (AN count at baseline AN count at current visit) / AN count at baseline \times 100% \geq 50/75/90/100%
- Abscess count at baseline \geq abscess count at the current visit
- Draining fistula count at baseline \geq draining fistula count at the current visit

where AN count is abscess count + inflammatory nodule count, and abscess count and fistula count are summed across all regions and are inclusive of all abscesses, inflammatory nodules and fistula that have previously undergone localized surgical or medical intervention and are no longer present. The baseline value for lesion count (including draining fistula count) and Hurley stage is the latest value on or before the randomization day (Day 1).

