- The third secondary endpoint, proportion of subjects who achieve at least 3 points reduction from baseline in NRS at Week 16 among participants with baseline NRS ≥4, comparing izokibep dosed QW to placebo dosed QW or Q2W.
- The third secondary endpoint, proportion of subjects who achieve at least 3 points reduction from baseline in NRS at Week 16 among participants with baseline NRS ≥4, comparing izokibep dosed Q2W to placebo dosed QW or Q2W.

If a null hypothesis is not rejected, p-values for subsequent hypotheses in the sequence will be reported as nominal, and will not be used to assess objectives or make determinations of efficacy.

For Part B, efficacy endpoints will be summarized by Period 1 and Period 2 separately. For Period 2, in general, no hypothesis test will be performed and p-value will not be reported. For binary endpoints, stratified tests will use the four strata from the randomization process. If a subject was incorrectly classified during the randomization process, the analysis will use the correct classification as recorded in EDC, not the classification used during randomization as recorded in IRT.

For each primary and secondary efficacy endpoint, the number and proportion of subjects achieving the endpoint in each treatment group will be reported by stratum and overall. Confidence intervals will be present with stratification (CMH weighting) and without stratification (Wald method). P-values will be reported for the stratified analysis. A bar graph showing the proportion of subjects achieving the endpoint for each treatment group along with the associated p-value will be produced. Results will also be listed.

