A stratified test of response rates will be used for the primary analysis. Within each of the four strata used for randomization, the response rate for each treatment group and corresponding standard error will be calculated. The difference in response rates (risk difference) will be calculated for each stratum. The common risk difference among the four strata and associated standard error will be estimated by combining the observed risk differences using Cochran-Mantel-Haenszel weighting. The estimated risk difference divided by the standard error will be used as the test statistic and a p-value calculated assuming that the test statistic follows a standard normal distribution under the null hypothesis. Analyses at earlier timepoints when data to calculate the HiSCR75 are collected will also be presented using the same methodology. P-values from earlier timepoints will be presented for descriptive purposes, not part of the alpha-preserving multiple testing strategy. No P-values after Week 16 will be presented.

Sample SAS code with stratification factors of comparing each dosing regimen of izokibep to the combined placebo group is given as following:

```
ods output commonpdiff = ;
proc freq data= ;
tables stratum * treatment * response / cmh commonriskdiff (test=mh cl=mh);
weight count / zeros;
run;
```

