 - Descriptive MMRM analyses will be performed by randomized treatment group, for change from baseline of IHS4 score and draining fistula count at Week 24 and Week 32. The change from baseline value will be used as the response variable, with baseline value, visit week, treatment, and treatment * visit week interaction included as predictors in the model. Estimated LSMean change from baseline, corresponding SE values, and 95% confidence intervals will be presented in the table summaries.

- The subgroup of subjects who were responders at Week 16 by AN count of 0, 1, or 2 (among those with Hurley stage II at baseline) will also be evaluated at Week 24 and Week 32 in the same manner as described for HiSCR75 responders.
- The subgroup of subjects who were non-responders at Week 16 by HiSCR75 will also be evaluated at Week 24 and Week 32 in the same manner as described for HiSCR75 responders.
- The subgroup of subjects who were non-responders at Week 16 by AN count of 0, 1, or 2 among those with Hurley stage II at baseline will also be evaluated at Week 24 and Week 32 in the same manner as described for the HiSCR75 responders.
- McNemar test will be used to evaluate the relationship between HiSCR75 response at Week 16 vs various response criteria at Week 32. P-values will be provided for descriptive purposes. The following response criteria at Week 32 will be used for this analysis:
 - o HiSCR75
 - o HiSCR90
 - HiSCR100
 - o HiSCR50
 - $\circ \quad \text{AN count of } 0, 1, \text{ or } 2$
- McNemar test will be used to evaluate the relationship between "AN count of 0, 1, or 2" response at Week 16 vs various response criteria at Week 32. P-values will be provided for descriptive purposes. The following response criteria at Week 32 will be used for this analysis:
 - o HiSCR75
 - HiSCR90
 - HiSCR100
 - HiSCR50
 - AN count of 0, 1, or 2

The following analyses will be done (by randomized treatment groups) for only the FAS subjects randomized to placebo who had least one dose of izokibep in Period 2 of the study AND who had a total AN count of \geq 5 at Week 16 and HS lesions present in at least 2 distinct anatomic areas (to correspond to the inclusion criteria), to address the question of how subjects respond to izokibep after 16 weeks of placebo, when they still meet original eligibility criteria:

- The baseline characteristics summary described in section 6.4.2 will be repeated for this analysis set at Week 16.

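### McNemar tests of HiSCR75 at Week 16 against HiSCR50, HiSCR90 or HiSCR100 at Week 32 confound threshold with time and can give small p-values when no subject changes

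*SAP*

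**What the plan says.** The tests belong to a block of SAP 6.6.7 that opens: "The following analyses will be done by all four randomized treatment groups for the FAS subjects who had at least one dose of izokibep". That dose must fall at Week 16 or later. The block's stated purpose is to learn whether subjects on izokibep from the start keep or add to their benefit after Week 16, and whether subjects who began on placebo gain further or catch up.

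Two McNemar series close the block.

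- First series: "McNemar test will be used to evaluate the relationship between HiSCR75 response at Week 16 vs various response criteria at Week 32". The SAP continues, "The following response criteria at Week 32 will be used for this analysis", and lists HiSCR75, HiSCR90, HiSCR100, HiSCR50 and an AN count of 0, 1 or 2.
- Second series: "McNemar test will be used to evaluate the relationship between 'AN count of 0, 1, or 2' response at Week 16", set against the same five Week 32 criteria.

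For both series, "P-values will be provided for descriptive purposes". Each series therefore has one pairing with the same criterion at both visits and four pairings with different criteria. The SAP does not say whether the test is exact or asymptotic, or how a result from a mixed pairing is to be read.

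SAP 2.4 defines the response levels together: "HiSCR50/75/90/100 is defined as meeting all three criteria below". The criteria are a percentage reduction in AN count, no increase in abscesses and no increase in draining fistulas. Only the percentage differs between levels.

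**The concern.** McNemar's test has one null hypothesis: the two paired proportions are equal. It is a test of change only if the same thing is measured twice. When HiSCR75 at Week 16 is paired with another HiSCR level at Week 32, two things differ at once, the visit and the threshold, and the test cannot separate them.

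The result can mislead in both directions. With nobody changing, the HiSCR50 pairing looks like gain and the HiSCR90 and HiSCR100 pairings look like loss. Conversely, if responses really deepened until the HiSCR90 rate at Week 32 equalled the HiSCR75 rate at Week 16, the test would show nothing. What is at stake is the reading of the maintenance data after Week 16, not the trial's main conclusions.

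**Working it through.** The plan gives no figure for these tests, so there is none to reproduce. The check holds every subject's lesion counts identical at Weeks 16 and 32 and asks what the tests would then report.

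**Inputs**

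- Group sizes (SAP 2.1): 56-57 in each izokibep group and 28-29 in each placebo-start group. The check uses 57 and 28. The analysed sets can be smaller, because a dose on or after Week 16 is required.
- Gap between HiSCR50 and HiSCR75: Protocol 2.2.1 reports about 50% clinical response with adalimumab at Week 12, and Protocol 9.5 reports HiSCR75 of 25% to 35% with adalimumab. Taking the first figure as HiSCR50 is an assumption. The gap is then 50 - 35 = 15 to 50 - 25 = 25 points. Carrying it over to izokibep is a second assumption. Using it for the placebo-start groups is a third, since those subjects are on placebo until Week 16 and the documents give no placebo HiSCR50 rate.
- The documents give no HiSCR90 or HiSCR100 rates, so the table below covers a range of gaps.

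**Step 1, nesting.** A subject who meets HiSCR100 meets HiSCR90, hence HiSCR75, hence HiSCR50. With counts unchanged, the discordant cells are (b, 0), where b is the number of subjects between the two thresholds.

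**Step 2, p-values.** Exact two-sided p = 2 × 0.5^b. Asymptotic p = P(chi-square with 1 df > b).

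- b = 4: exact 0.125, asymptotic 0.046
- b = 5: exact 0.0625, asymptotic 0.025
- b = 6: exact 0.031, asymptotic 0.014

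So p < 0.05 needs 4 subjects (asymptotic) or 6 (exact).

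**Step 3, by gap and group size.** b = n × gap, rounded; p-values are exact / asymptotic.

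| Gap (points) | n = 57: b | p | n = 28: b | p |
|---|---|---|---|---|
| 5 | 3 | 0.25 / 0.083 | 1 | 1.00 / 0.317 |
| 10 | 6 | 0.031 / 0.014 | 3 | 0.25 / 0.083 |
| 15 | 9 | 0.0039 / 0.0027 | 4 | 0.125 / 0.046 |
| 20 | 11 | 0.0010 / 0.0009 | 6 | 0.031 / 0.014 |
| 25 | 14 | 0.00012 / 0.00018 | 7 | 0.016 / 0.008 |

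**Step 4, HiSCR90 and HiSCR100.** A simulation with frozen counts assumed a baseline AN of at least 5 with mean 14, and three assumed distributions for the share of lesions remaining. It ignored the abscess and fistula conditions. The share of runs with asymptotic p < 0.05 (exact test in brackets) was:

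- n = 57: HiSCR90 0.93-1.00 (0.72-0.98); HiSCR100 0.98-1.00 (0.87-1.00)
- n = 28: HiSCR90 0.47-0.81 (0.13-0.49); HiSCR100 0.63-0.95 (0.25-0.77)

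**Step 5, pairings with AN count 0-2.** These are not nested with HiSCR75. A fall from 5 to 2 is a 60% reduction: it meets AN 0-2 but not HiSCR75. A fall from 20 to 4 is an 80% reduction: it can meet HiSCR75 but not AN 0-2. Discordance runs both ways and partly cancels. In the same simulation, HiSCR75 against AN 0-2 gave asymptotic p < 0.05 in 0.06-0.12 of runs at n = 57 and 0.02-0.07 at n = 28. In general, then, the direction of the distortion in the AN pairings is not fixed. The one exception is AN 0-2 at Week 16 against HiSCR100 at Week 32: a 100% reduction means an AN count of 0, so that pairing is nested.

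**Step 6, same criterion.** For HiSCR75 against HiSCR75, or AN 0-2 against AN 0-2, no change gives b = c = 0 and p = 1 by convention. These tests behave as intended.

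**The case against.** The strongest defence is that little depends on these tests. They are labelled descriptive, confined to Period 2 and outside the testing sequence of SAP 6.6. SAP 6.6.7 also answers the maintenance question directly, with Week 24 and Week 32 response rates and Clopper-Pearson intervals among Week 16 responders and non-responders. All of that stands, and it limits the importance of the point. It does not rescue the mixed pairings: a descriptive p-value should still describe the quantity of interest, and these mostly count subjects between two thresholds.

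Three stronger readings are tempting, and the documents do not support them.

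- *That all the planned McNemar tests are faulty.* Each series includes a valid same-criterion test, and most AN pairings lack the one-way structure.
- *That a small p-value is assured without change.* It is likely in the larger groups, but in the groups of 28-29 it depends on the gap and on which version of the test is used.
- *That the tests break a rule against p-values after Week 16.* SAP 6.6 does say of Period 2 that "no hypothesis test will be performed and p-value will not be reported", but the sentence is qualified as holding in general. The statement in SAP 6.6.1, "No P-values after Week 16 will be presented", closes the description of the stratified comparison with placebo, whereas the McNemar tests are within-group. SAP 6.6.7 expressly provides for its p-values. A specific exception to a general rule is not a contradiction.

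**Conclusion.** The point holds for HiSCR75 at Week 16 against HiSCR50, HiSCR90 and HiSCR100 at Week 32. The null hypothesis of equal proportions is false there by construction, and the p-value cannot show whether benefit was sustained or added. The nesting and the thresholds of 4 or 6 subjects need no assumption about rates. The quoted sizes rest on the assumed 15 to 25 point gap and on nearly full groups; the HiSCR90 and HiSCR100 results rest on assumed lesion distributions. The AN pairings in both series share the fault of mixing criteria, generally without a fixed direction.

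Impact is low. No primary or secondary test, error rate or estimate is affected, and it should not be inferred that the efficacy conclusions are at risk.

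**What to change.** In both series of SAP 6.6.7, keep McNemar's test only where the criterion is the same at both visits. Suggested text:

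> Within each randomized group, McNemar's test will compare HiSCR75 at Week 16 with HiSCR75 at Week 32, and AN count 0-2 at Week 16 with AN count 0-2 at Week 32. Pairings of different criteria will be shown as two-by-two tables of counts and percentages, without p-values.

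The SAP should also name the version of the test, since exact and asymptotic results fall on different sides of 0.05 at 4 or 5 one-way discordant pairs.

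The cost is an edit to a final SAP and the loss of p-values for 8 of the 10 planned pairings. Little information is lost: the cross-tabulations show how many Week 16 responders reach each level at Week 32, and the planned rates with confidence intervals remain.
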